## **PARTNERS HUMAN RESEARCH COMMITTEE DETAILED PROTOCOL**

### **Electronic Tools to Increase Recognition and Improve Primary Care Management for Hypertension in Chronic Kidney Disease**

**P.I.: [name] M.D., M.P.H.**

#### **I. BACKGROUND AND SIGNIFIGANCE**

Prevalence, Outcomes and Cost of Chronic Kidney Disease: Chronic kidney disease (CKD) is prevalent, afflicting 26 million Americans, and is a condition associated with high morbidity and mortality. In addition, CKD is costly. The average cost per person per year is about \$20,000 and Medicare costs for ESRD total \$26.8 billion. CKD Diagnosis, Monitoring, and Treatment Must Be Improved in Primary Care Clinics: There are effective approaches to monitoring and treatment that must be disseminated broadly in order to cut costs and to save lives. Dissemination efforts must focus on primary care clinics because 95% of patients with CKD have early disease and are cared for by primary care physicians (PCPs). Only 15% of patients whose estimated glomerular filtration rate (eGFR) is less than 60 mL/min/1.73m^2 are aware that they have CKD, so it is especially important that PCPs become aware of the diagnosis early. Furthermore, there is evidence that CKD is under-diagnosed by PCPs. Data from our 15 primary care clinics showed that only 15% of patients with CKD had a documented diagnosis of CKD and only 40% had a urine albumin test. Hypertension Control in CKD Improves Outcomes: Hypertension (HTN) is one of the most, if not the most, important risk factor for long-term outcomes such as kidney failure, cardiovascular events, and death. A met analysis of three large cohorts of CKD patients without diabetes concluded that maintaining blood pressure below 140/90 mmHg decreases risk of these outcomes significantly. Several guidelines have been issued to emphasize the importance of HTN control in CKD. Evidence-based Management by PCPs for HTN in CKD: Many effective approaches for recognition of CKD and treatment of uncontrolled HTN in CKD are appropriate for the primary care setting. Lifestyle Change Counseling: Lifestyle change is recommended for all patients with uncontrolled HTN. The role of the PCP as counselor for lifestyle change is accepted and welcomed by both patients and PCPs. Lack of time is a common barrier, but when PCPs perform brief counseling it tends to be successful, as shown in the literature on tobacco cessation. Anti-hypertensive Medication Initiation and Intensification: Evidence-based guidelines recommend certain anti-hypertensive agents in CKD, either an angiotensin converting enzyme inhibitor or angiotensin receptor blocker (ACE/ARB). The UK NICE guidelines specify a protocol for initiation and intensification of medications based on demographic characteristics. Efforts to simplify patients' medication regimens and provide patient education are proven to be effective in reducing blood pressure HTN in CKD Is Under-recognized and Suboptimally Managed, but CDS Has Shown Potential in Clinical Trials of the Non-CKD HTN Population: Nationally representative data show that 52% of CKD patients have diagnosed HTN, 19% have preHTN, and 16% have undiagnosed HTN. Treatment rates are suboptimal given the fact that less than 40% of CKD patients with uncontrolled HTN are prescribed anti-hypertensive medications. HTN control rates, cited as 48% to 72% across studies, are also suboptimal. A large meta-analysis of clinical decision support (CDS) for HTN in a non-CKD population showed a positive result, but with a small

## II. SPECIFIC AIMS

**Hypothesis:** The mean systolic blood pressure of the CKD population can be decreased by an intervention with three innovative features: 1) methods to synthesize EHR data in order to identify under-diagnosed chronic conditions, 2) iterative improvement in CDS content through human factors methods to maximize the “informativeness” of the CDS, and 3) the use of behavioral economic principles to create behavioral “nudges” internal and external to the CDS.

**Specific Aim 1:** To develop and validate the intervention.

**Specific Aim 1a:** To develop and validate the CDS that will: 1) synthesize existing laboratory tests, medication orders, and vital sign data; 2) increase recognition of CKD, 3) increase recognition of uncontrolled HTN in CKD patients; and 4) deliver evidence-based CKD and HTN management recommendations.

**Specific Aim 1b:** To improve the design and content of the CDS using human factors methods, specifically usability testing.

**Specific Aim 1c:** To develop a “wrap-around” intervention including two behavioral “nudges”: 1) pre-checked default orders, and 2) an email to obtain commitment from PCPs to obtain their commitment to follow the CDS recommendations.

**Specific Aim 2:** To test the effectiveness of the intervention.

**Specific Aim 2a:** To evaluate whether the intervention developed in Aim 1 significantly decreases mean systolic blood pressure in a population of CKD patients with blood pressure  $> 140/90$ ,  $N=2,350$  ( $N$  derived from EHR data about primary care patients at 15 clinics). We will evaluate the effectiveness of the intervention in a pragmatic, cluster-randomized controlled trial, randomized at the level of the physician (185 PCPs). Secondary outcomes will include hypertension-specific process measures, such as treatment intensification.

**Specific Aim 2b:** To evaluate whether the intervention improves process measures for quality of CKD care including: documented CKD diagnosis, annual serum creatinine test, and annual urine albumin test. We will also examine process measures related to CKD care. We will use multivariable logistic regression to account for clustering by PCP using a multilevel statistical regression model, as implemented in the SAS package through the GLIMMIX procedure.

**Specific Aim 2c:** To perform a cross-over study in order to evaluate the effect of the intervention on PCP behavior and PCPs' intention to change behavior, as measured by a validated 12-item questionnaire.

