#### **Inclusion of Women and Minorities**

Women will be represented in this study, reflecting the patient population of the BWH primary care practices and the physician population of BWH; women comprise over 50% of patients in these practices. Minorities also are fully represented in this study in proportion to their presence in these primary care practices and in proportion to their presence in the BWH physician and specialist community. The practices serve an ethnically and socioeconomically diverse patient population. Approximately 16% percent of BWH patients are Latino and 29% are Black. About 1.5% of BWH patients are Asian. Definitions of patients' race and ethnicity will be based on self-report at the time of hospital registration. By promoting uniformly high standards of patient care, our interventions may lessen disparities in care.

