### IV. SUBJECT ENROLLMENT

Randomization and Enrollment: This study will utilize a matched-pair cluster randomized design with the intervention on the cluster level, and the main outcome (6 month minus baseline change in SBP) measured at the patient level. We will have 174 clusters (made up of 185 clinicians) in the study. We will match pairs of clusters with similar number of patients and prior year mean blood pressure of patients in the cluster. One cluster in each pair will be randomized to the intervention and unit one to usual care. Patients will be electronically identified and included in the study over the course of 12 months. Patients seen by PCPs during the pilot study will be excluded. Retrospective data indicates that 70% of patients have a follow-up around 6 months. Outcomes assessment will occur at 180 days (+/- 60 days). After the 12-month enrollment period ends, data collection will continue for 6 months so that those enrolled toward the end of the enrollment period will have a full 6 months to complete any interventions ordered by the PCP. A small subset of PCPs will be enrolled in a pilot study for approximately one month, as described below in study procedures Aim 1b. Clinical outcomes will be recorded and reviewed every month over the course of the trial.

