**Specific Aim 2 & 2a Procedures:**

**Setting:** The Brigham and Women's Primary Care Practice-Based Research Network (BWPC PBRN) is one of 155 PBRNs nationally certified by the Agency for Healthcare Research and Quality (AHRQ). The BWPC PBRN is a network of 15 practices which includes hospital-based practices, community-based practices, and community health centers affiliated with Brigham and Women's Hospital. The network includes 185 primary care physicians that care for approximately 150,000 patients.

**Subjects:** All patients over the age of 18 who have a visit with a PCP at one of the intervention practices during the 2 years preceding the study period will be eligible. We are able to utilize data from the past five years stored in the EHR to identify CKD patients with uncontrolled HTN. The first inclusion criteria will be CKD, defined as two prior eGFR 16-59 mL/min/1.73m^2 separated by 90 days, as calculated by CKD-EPI, or two prior UACR >30mg/g. The second inclusion criteria will be uncontrolled hypertension, defined as at least two SBP >140 mmHg within the 2 years preceding the study period. We will exclude all patients who are currently pregnant. The CDS will review lab data starting five years before the visit to determine whether the patient has CKD using the logic described above. If the patient has CKD, the CDS will search BP data starting one year before the visit to determine whether the patient has had at least two SBP > 140 mmHg.

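### Practice enters neither the pair matching nor the one stated model; a random practice level would recover some precision, mainly for the process measures

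*Combined protocol and SAP*

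**What the plan says.** The setting (Section V, Specific Aim 2 & 2a Procedures) is "a network of 15 practices which includes hospital-based practices, community-based practices, and community health centers". Clusters are PCPs or small groups of them: "We will have 174 clusters (made up of 185 clinicians) in the study" (Section IV). The matching rule in Section IV is "We will match pairs of clusters with similar number of patients and prior year mean blood pressure of patients in the cluster", followed by "One cluster in each pair will be randomized to the intervention and unit one to usual care". Practice is neither a matching factor nor a stratum.

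The only regression model in the document is in Section II, Aim 2b: "We will use multivariable logistic regression to account for clustering by PCP using a multilevel statistical regression model", to be fitted in SAS GLIMMIX. It names no practice level, no matched pair and no list of covariates. Section VI holds outcome tables and gives no model for the primary outcome, change in SBP at 6 months.

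**The concern.** Whether a creatinine or urine albumin test is ordered, a diagnosis is entered or an e-consult is requested plausibly depends on how a site works as well as on the individual PCP. Neither matching factor speaks to these outcomes, and a pair can straddle two kinds of practice. Some practices will then contribute more clusters to one arm than to the other by chance.

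A model with PCP as its only level carries the between-practice variation inside the between-PCP variance. The standard error is honest but larger than it need be, and the estimate is not adjusted for the practice split that actually occurred. The plan drew its clinicians from a 15-practice roster (Section III), so each PCP's practice should be on hand before randomisation.

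**Working it through.** **Inputs from the documents.** K = 174 clusters, hence 87 pairs; 15 practices; N = 2,350, so 2,350/174 = 13.5 patients per cluster; 70% with follow-up near 6 months, so 1,645/174 = 9.45 per cluster for SBP. Network base rates are 15% for a documented CKD diagnosis and 40% for a urine albumin test (Section I). There is no power calculation to reproduce: N is "derived from EHR data about primary care patients at 15 clinics", and no SD, ICC, alpha or power is given.

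**Assumptions.** Practice sizes: 14 of 12 clusters and one of 6 (14 × 12 + 6 = 174), with each cluster inside one practice. Process measures: total ICC 0.05, 0.10 or 0.20, half between practices. SBP: total ICC 0.02 or 0.05, a quarter or a half between practices. SD of SBP change: 18 mmHg. Pairing ignores practice. Calculations are on a linear scale with known variance components.

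**1. What the assumed ICCs mean.** Between-practice SD = √(practice ICC × p(1 − p)). At p = 0.40, practice ICCs of 0.025, 0.05 and 0.10 correspond to SDs of 7.7, 11.0 and 15.5 percentage points; at p = 0.15, to 5.6, 8.0 and 11.3 points.

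**2. Chance imbalance.** In 20,000 random pairings and allocations, at least one practice split 9:3 or worse in about 85% of runs; the expected number is about 1.9 of 15. For SBP, the SD of the arm difference due to practice imbalance is 18 × √(4/174 × practice ICC): 0.27, 0.39 and 0.61 mmHg at 0.01, 0.02 and 0.05.

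**3. Validity.** Simulated type I error of a PCP-level comparison that ignores practice was 4.9% to 5.1% (practice ICC 0.02 and 0.05).

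**4. Precision.** Let ρp be the practice ICC, ρc the PCP ICC, and w = ρc + (1 − ρp − ρc)/m.
- Practice ignored: V0 = (4/K)(0.94ρp + w). The 0.94 arises because the 87:87 split is fixed: simulated sum of squared share differences 0.0216, against 4/174 = 0.0230.
- Fixed practice effects: Vf = (4/K) × w × 172/158, a factor of 1.089.
- Random practice level: the treatment sum of squares, 174/4 = 43.5, divides into about 43.5/1.089 = 39.96 within and 3.54 between practices. Vr = 1/[39.96/w + 3.54/(w + 12ρp)].

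Change in SE:

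| Outcome | Total ICC | Practice share | w | Fixed | Random |
|---|---|---|---|---|---|
| Process | 0.05 | half | 0.0953 | −6.5% | −7.5% |
| Process | 0.10 | half | 0.1166 | −11.9% | −12.5% |
| Process | 0.20 | half | 0.1592 | −17.3% | −17.7% |
| SBP | 0.02 | quarter | 0.1187 | +2.3% | −0.5% |
| SBP | 0.02 | half | 0.1137 | +0.3% | −1.8% |
| SBP | 0.05 | quarter | 0.1380 | +0.2% | −1.9% |
| SBP | 0.05 | half | 0.1255 | −4.2% | −5.5% |

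Example, first row: V0 = 0.02299 × (0.0235 + 0.0953) = 0.002731; Vr = 1/(419.3 + 9.0) = 0.002335; √(0.002335/0.002731) = 0.925.

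Computing the variances allocation by allocation and averaging agrees with the table to within a point. The rounded random-level figures used below are about 8%, 12% and 17% for process measures and 1% to 6% for SBP.

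**5. No practice variance.** Fixed effects would still multiply the variance by 1.089, taking a test with 80% power to 76.6%. With known components, a random level loses nothing.

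**The case against.** The strongest reply is that nothing here is invalid. PCPs are randomised, practice variance is absorbed into the PCP variance, and type I error is nominal. A reader might infer bias or an inflated error rate from the omission of practice; the simulation shows neither. The 85% figure also sounds worse than it is: about two practices out of 15 splitting 9:3 is ordinary random allocation, and the standard error already covers it. This stands.

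A reader might also infer that practice is missing from every comparison. The documents do not support that. The quoted model concerns the Aim 2b process measures, and no SBP model is written from which practice could be shown to be excluded. Even the Aim 2b model is called multivariable without a covariate list, so practice is unspecified, not ruled out. Nor do the documents show that the practices differ greatly: three types are named and the patient population is called diverse overall, but no practice-level rates, sizes or blood pressures are given.

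For SBP, matching on prior-year blood pressure and analysing change from baseline should already remove part of any practice difference, and the calculation credits neither. Fitting 15 practice effects to SBP gives no gain in three of the four assumed settings. If the 87 pairs are fitted as well, the variance factor rises to about 1.20 and the SBP gain disappears throughout. That defeats fixed effects as the remedy. It does not defeat a random level, and it does not reach the process measures, for which nothing in the design stands in for practice.

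**Conclusion.** The point holds as one of precision and pre-specification. Practice is absent from the matching rule and from the only stated model, and nothing elsewhere in the plan brings it in. A random practice level would lower the SE by about 8%, 12% or 17% for process measures at total ICCs of 0.05, 0.10 or 0.20, half between practices. For SBP it would lower it by about 1% to 6% at ICCs of 0.02 to 0.05, against a 2% loss to a 4% gain with fixed effects.

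Every ICC, the practice sizes and the SD are assumptions, and the percentages are linear-scale approximations to a logistic model. The gain is nil if practice variance is near zero, and smaller if pairs happen to fall within practices. The claim does not extend to bias, to a false-positive problem, or to a demonstrated loss in the primary analysis.

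**What to change.** In the Aim 2b GLIMMIX model, add practice as a random intercept above PCP, and use the same structure for the Table 1 process outcomes (medication, metabolic panel, e-consult). For rare outcomes where this does not converge, name practice type (hospital-based, community-based, health centre) as the fallback covariate. When the SBP model is written, include the same random level in preference to 15 fixed effects, and state there how the matched pair enters.

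The cost is a few sentences in the analysis section and one extra variance parameter, for a variable that should already be held for every PCP. The drawback is that 15 practices estimate that variance imprecisely, so the plan should say what is done if the estimate is zero. The odds ratio will also be conditional on practice as well as PCP, which the report should state.

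### The only stated model (Aim 2b) clusters on the individual PCP, while Section IV randomises 174 clusters of clinicians in matched pairs; the unit and the pairing should be aligned, though the likely effect is modest

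*Combined protocol and SAP*

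**What the plan says.** The protocol describes the randomised unit in two ways.

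- Section II, Aim 2a: the trial is "randomized at the level of the physician (185 PCPs".
- Section IV: "We will have 174 clusters (made up of 185 clinicians) in the study". The design is spelled out there: "This study will utilize a matched-pair cluster randomized design with the intervention on the cluster level". On matching: "We will match pairs of clusters with similar number of patients and prior year mean blood pressure of patients in the cluster". On allocation: "One cluster in each pair will be randomized to the intervention", with the other cluster receiving usual care.

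One regression model is stated. It is in Section II, Aim 2b, after a list of binary CKD process measures. It is a multivariable logistic model in SAS GLIMMIX that will "account for clustering by PCP using a multilevel statistical regression model". Its covariates are not listed.

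Section VI (Biostatistical Analysis) tabulates outcomes, metrics and time points. It names no regression model, no cluster term and no pair term, either for the primary outcome (change in systolic blood pressure) or for any secondary outcome.

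**The concern.** With 185 clinicians in 174 clusters, PCP and randomised cluster cannot be the same thing throughout. Clinicians in one cluster are always allocated together. A random effect for PCP alone treats them as separately randomised, which makes the standard error too small if their patients' outcomes are correlated. The pairing also restricts the randomisation, and leaving it out of the analysis generally makes the standard error too large when the matching works.

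Two things are at stake: the precision claimed for the Aim 2b comparisons, and a choice left open to the analyst. The documents support three counts of independent units (185 PCPs, 174 clusters, 87 pairs) and do not say which governs inference. If the Aim 2b approach were carried over to the primary outcome for want of another model, the mismatch would go with it.

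**Working it through.** The plan gives no power calculation, ICC or standard error, so there is no figure of its own to reproduce. The check is count arithmetic followed by an illustration under stated assumptions.

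**Counts (from the documents).**
- Pairs: 174/2 = 87. This is derived, not printed.
- Clinicians beyond one per cluster: 185 - 174 = 11, so at least one cluster has more than one clinician.
- Patients: 2,350 (Aim 2a, "derived from EHR data about primary care patients at 15 clinics"). Section IV adds: "Retrospective data indicates that 70% of patients have a follow-up around 6 months". That gives 0.70 × 2,350 = 1,645.
- Patients per clinician, m: 1,645/185 = 8.89, or 2,350/185 = 12.70.

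**Assumptions (not in the documents).**
- ICC 0.02 to 0.10.
- Equal numbers of patients per clinician.
- The 11 surplus clinicians form 11 two-clinician clusters, so 22 of 185 (12%) share a unit.
- The whole ICC is shared by clinicians in the same cluster. This is the maximum for that layout.
- Matching explains a fraction f of between-cluster variance, with f from 0.10 to 0.50.

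**Step 1: wrong unit.** Design effect DE = 1 + (A - 1) × ICC, where A = Σm²/Σm.
- With PCP as the unit, A = m.
- With cluster as the unit, A = (163 + 11 × 4)m/185 = (207/185)m.

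The PCP model understates the SE by 1 - √(DE_PCP/DE_cluster). Example at 2,350 patients and ICC 0.05: DE_PCP = 1 + 11.70 × 0.05 = 1.585; DE_cluster = 1 + 13.21 × 0.05 = 1.661; √(1.661/1.585) = 1.024; understatement 2.3%.

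**Step 2: pairs ignored.** Cluster-mean variance is v = ICC + (1 - ICC)/m. As a simplification, m per clinician is used here too. Ignoring pairs overstates the SE by √(v/(v - f × ICC)) - 1. Example at 2,350 patients, ICC 0.10 and f = 0.50: v = 0.10 + 0.90/12.70 = 0.1709; √(0.1709/0.1209) = 1.189; overstatement 18.9%.

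**Step 3: net.** Divide the step 2 ratio by the step 1 ratio √(DE_cluster/DE_PCP). For the last example: 1.189/1.034 = 1.150, or 15.0% too large.

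| Patients | ICC | SE too small, wrong unit | SE too large, pairs ignored (f = 0.10 / 0.50) | Net (f = 0.10 / 0.50) |
|---|---|---|---|---|
| 1,645 | 0.02 | 0.90% | 0.78% / 4.08% | -0.13% / +3.14% |
| 1,645 | 0.05 | 1.84% | 1.63% / 9.07% | -0.24% / +7.06% |
| 1,645 | 0.10 | 2.83% | 2.58% / 15.35% | -0.32% / +12.09% |
| 2,350 | 0.02 | 1.20% | 1.05% / 5.58% | -0.17% / +4.31% |
| 2,350 | 0.05 | 2.30% | 2.07% / 11.83% | -0.28% / +9.25% |
| 2,350 | 0.10 | 3.31% | 3.06% / 18.90% | -0.35% / +14.97% |

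**Sensitivity to grouping.** The documents do not say how clinicians are grouped. In the extreme case of one 12-clinician cluster, A = (173 + 144)m/185 = (317/185)m. Before any allowance for pairing, the correct SE is then 5% (1,645 patients, ICC 0.02) to 19% (2,350 patients, ICC 0.10) larger than the PCP model's. At 2,350 patients and ICC 0.05, the actual type I error of a nominal two-sided 5% test would be 8.4%.

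**Degrees of freedom.** The two-sided 5% t critical value is 1.973 with 183 df (PCPs), 1.974 with 172 df (clusters) and 1.988 with 86 df (pairs).

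**The case against.** The strongest case on the other side has four parts.

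- **The model is not the primary one.** It is logistic and serves the Aim 2b process measures, whereas the primary outcome is a continuous change. This stands. A reader might infer that the primary analysis uses the wrong unit. The documents do not support that, because for the primary outcome the specification is absent, not wrong.
- **The two effects oppose each other.** This also stands. A reader might infer inflated type I error. In the two-clinician layout the net is a fraction of a percent too small at worst and otherwise conservative. Even the step 1 effect requires that outcomes correlate across clinicians in a cluster; sharing an arm does not create that correlation. Material inflation needs clinicians concentrated in few clusters, which the documents neither state nor exclude.
- **PCP may be shorthand for the randomised cluster.** Section III says the clinician list includes physician assistants and nurse practitioners and aims at stable patient panels, so clinicians in one cluster might share a panel. This is possible, but Aim 2a attaches 185 to PCPs and Section IV separates 185 clinicians from 174 clusters. The text does not equate the two.
- **The pair term is not a clear gain.** No document shows that the matching factors predict outcomes such as CKD diagnosis or albumin testing, and the unlisted covariates might include those factors. Eighty-seven fixed pair effects in a logistic model with about 9 to 13 patients per clinician would be a real trade-off. This stands and limits how the pairing should be handled.

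**Conclusion.** The point holds as a mismatch of specification with a modest likely effect. The randomised unit is stated in two ways, the only stated model uses the one that disagrees with the detailed randomisation text, and the pairing enters no stated analysis. The mismatch is shown for Aim 2b and would reach the primary outcome only if that model were carried over.

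Under the assumptions above, the wrong unit alone understates the SE by about 1-3%, ignoring pairs alone overstates it by about 1-19%, and together the SE runs from about right to about 15% too large. These figures depend on an assumed ICC, assumed matching strength and an assumed grouping of clinicians. The structural mismatch does not. The case for acting is that the unit of inference should be fixed before analysis and should follow the randomisation; it does not rest on a demonstrated false-positive risk.

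**What to change.** 1. Reconcile Section II (Aim 2a) with Section IV so that both give 174 clusters in 87 pairs as the randomised units, and say how the 185 clinicians are grouped into clusters.
2. In the Aim 2b GLIMMIX model, use the randomised cluster instead of the PCP as the random-effect subject.
3. State a model for the primary systolic blood pressure outcome, with the same cluster as its unit, and apply that unit to the other comparisons between arms.
4. Reflect the matching through a random pair effect or by adjusting for the two matching variables (cluster patient count and the previous year's mean blood pressure). Do not use 87 fixed pair effects in the logistic models. Choose the approach and its degrees of freedom in advance.

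The cost is a few lines of text and a change to the model statement, with no new data, patients or procedures. The downside is slightly fewer degrees of freedom: even at 86 df the critical value is 1.988 against 1.973, so intervals widen by about 0.8% (1.988/1.973 = 1.008) before any gain from the matching.
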